Blood Sample Storage. Blood samples will be stored indefinitely at the Hemophilia Center of Western PA under the control of [name]. Samples will be labeled with code numbers, and information linking the code numbers to the subjects' identities will be kept in a separate, locked file at the Hemophilia Center.

Adverse events. The analysis of adverse events, including allergic reaction, thrombosis, and other bleeding, will be based on the number of subjects with adverse events, and incidence rates will be calculated as the number of subjects with an event divided by the number of subjects exposed to drug. Subjects with multiple events will be counted only once in the numerator. For analysis, the highest-grade severity will be considered, and for analysis of duration, the multiple episodes will be summed. Adverse events will be summarized, and each event reported by a subject will be counted repeatedly. The corresponding incidence rates for adverse event episodes will be calculated by the number of adverse event cases over the number of doses. Adverse event incidence rates will be categorized by body system, relationship to study drug, severity of adverse event, age, sex, time of onset of adverse event, and duration of adverse event. Laboratory variables will be analyzed by descriptive statistics.

Sample Size and Power for Pilot Study

Pilot studies require a minimum of nine subjects to prevent an unnecessarily high number of subjects to receive a study drug, but a high enough number to provide insight into safety and efficacy parameters for a study drug.⁴¹ The minimum planned sample size of 20 evaluable subjects also provides adequate power to

evaluate the success and feasibility of the study.⁴¹ The study is considered successful if treatment of fewer than or equal to 6 of the 20 subjects is assessed ineffective or unsafe. The study is considered feasible if procedures, i.e. recruitment, randomization, and study drug administration can be performed successfully.

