4.6 Risk/Benefit Assessment

Risk to Subjects

There are risks associated with the study drug and having blood drawn. rVWF and/or TA will be administered at delivery and on days 1 and 2 postpartum. All subjects will be asked to report any safety problems or side effects associated with administration of study drug(s).

Risk of Blood Draw

There may be discomfort with drawing blood, which is common, occurring in up to 25%, or 25 in 100 people: this may include pain, lightheadedness, fainting, bruising, or bleeding or infection in the tissue around the vein. This may be alleviated or reduced by applying pressure to the blood draw site for 5 minutes, and assuming a recumbent position, i.e. lying on your back with your head flat and knees bent, if lightheaded.

Risks of Study Drugs:

rVWF and TA

Allergic-type reactions are rarely reported for rVWF, at similar doses as in this study (e.g. 75 IU/kg), and thus, the risk is expected to be uncommon, occurring in < 0.001% or less than 1 in 100,000 people. Allergic reactions for TA are expected to be rare in this study, occurring in <.001%, or less than 1 in 100,000 people. Allergic reactions could include chills, fever, nausea and vomiting, or rarely may include, in decreasing order of severity, death, anaphylaxis (life-threatening difficulty breathing), low blood pressure, heartbeat irregularity, increase in body fluids, paresthesias (numbness or prickling sensation), urticaria (hives), chest tightness, rash, pruritus (itching), edema (swelling), fever, and/or chills. Should these symptoms occur, benadryl, a medication which reduces inflammation, may be given, with close monitoring of these symptoms. Benadryl may cause drowsiness, dizziness or low blood pressure. Subjects will be monitored for these symptoms. No one with a history of allergy (hypersensitivity), an allergic reaction or anaphylaxis associated with either recombinant von Willebrand factor (rVWF, Vonvendi®) or tranexamic acid (TA, Cyclokapron®) will be enrolled. Subjects will be monitored closely for early symptoms and signs of allergic or hypersensitivity reactions, including fever, chills, hives, tachycardia, chest discomfort, and anaphylaxis. Any subject who develops signs or symptoms of an allergic type reaction or anaphylaxis during administration of either study drug will immediately have that study drug stopped and appropriate medical care initiated.

Risk of Thromboembolism/Thrombogenicity

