In addition to halting enrollment and further treatment, such an event will be handled as a serious adverse event (SAE) and reported in an expedited time frame to the FDA. The data concerning the event and subject with input from the site HTC Co-Investigator will be reviewed by the DSMC along with all other available data to determine appropriate follow-up, with a decision to continue enrollment and treatment of subjects at that time. If the decision is made to discontinue the study, the Co-Investigators will be notified and the appropriate final study evaluations (Final Visit) will be performed on all subjects enrolled in the study at that time.

Additionally, the following may also stop further subject enrollment and treatment.

- The DSMC warrants temporary suspension of enrollment for further review of data generated to date.
- The PI determines that a medically important event warrants further evaluation by the DSMC. In these cases the required follow-up as determined by the PI and/or DSMC will be performed. The DSMC will determine if it is appropriate to reinitiate enrollment in the study. The IRB will be informed of such decisions.

Local Adverse Event Reporting

All adverse events experienced by study subjects from the time of dosing until 30 days after administration is to be recorded on the CRF, regardless of the severity of the event or its relationship to study treatment.

The serious AE reporting procedures are based on the “Cancer Therapy Evaluation Program: Common Terminology Criteria for Adverse Events” (CTCAE) v 4.03, June 14, 2010.⁴⁰ Subjects will report to HTC co-investigator or to the HTC nursing coordinator, any AE or SAE. AE's will be classified as mild (does not interfere with routine activities), moderate (interferes somewhat with routine activities), or severe (impossible to perform routine activities). The following algorithm will be used to assess the causality of all AE's:

- Not related: The event can readily be explained by factors not involving rVWF and/or TA, and a temporal relationship with rVWF and/or TA, does not exist.
- Possibly related: A clinical event, including laboratory test abnormality, with a reasonable time sequence to administration of rVWF and/or TA, but which could also be explained by concurrent disease or other drugs or chemicals. Information on drug withdrawal may be lacking or unclear.

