- Probably related: The temporal relationship between the administration rVWF and/or TA is compelling, and the event cannot be explained by the subject's medical condition or other therapies.
- Related: The event follows a reasonable temporal sequence from administration of rVWF and/or TA follows a known or suspected response pattern to rVWF and/or TA, is confirmed by improvement upon stopping the agent (de-challenge) and reappears upon repeated exposure to rVWF and/or TA.

All AEs, regardless of severity, will be followed up by HTC Investigator until satisfactory resolution. All subjects experiencing AEs will be monitored until symptoms subside and any abnormal laboratory values have returned to baseline, or until there is a satisfactory explanation for the changes observed, or until death, in which case a full pathologist's report will be supplied, if possible. Withdrawal from the clinical study and therapeutic measures shall be at the discretion of the investigator.

As required by the University of Pittsburgh Institutional Review Board, if there is an unexpected, serious internal adverse event (life threatening or fatal) that is determined to be associated with rVWF and/or TA, it will be reported to the IRB within 24 hours. If the event is not serious, unexpected or related to either agent, it will be reported within 5 days. External adverse events that are unexpected, related to either agent and determined to place the subject at greater risk than previously recognized, will be reported within 10 working days of notification.

Adverse Event (AE) Reporting at sites:

All events must be assessed to determine the following:

- If the event meets the criteria for an SAE
- The relationship of the event to study treatment
- The severity of the event

An AE is any untoward medical occurrence in a subject in whom a pharmaceutical product is administered and that does not necessarily have a causal relationship with this treatment. An AE can therefore be any unfavorable and unintended sign (including an abnormal laboratory finding), symptom, or disease temporally associated with the use of a pharmaceutical product, whether or not related to the pharmaceutical product.

A serious adverse event (SAE) is any untoward medical occurrence that at any dose:

- results in death

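### Causality is rated once for rVWF and TA together, on two scales that disagree, so the planned table by relationship cannot isolate TA

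*Combined protocol and SAP*

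**What the plan says.** **First scale** (Section 5.0, Local Adverse Event Reporting). It is introduced by "The following algorithm will be used to assess the causality of all AE's". All four levels name rVWF and/or TA as one exposure:
- *Not related*: the event is readily explained by other factors, "and a temporal relationship with rVWF and/or TA, does not exist". Both conditions must hold.
- The next level, *possibly related*, reads "A clinical event, including laboratory test abnormality, with a reasonable time sequence to administration of rVWF and/or TA", even though concurrent disease or other drugs could also explain it.
- *Probably related*: "The temporal relationship between the administration rVWF and/or TA is compelling", and nothing else explains the event.
- *Related*: adds a known or suspected response pattern, improvement on stopping and return on re-exposure.

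**Second scale** (Section 5.0, Safety Classifications and Relationship of Events to Study Treatment). Its levels are *unrelated*, *unlikely*, *possibly* and *related*, for AEs and SAEs, judged against study treatment undivided.

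**Analysis** (Section 3.3, Adverse events). "Adverse event incidence rates will be categorized by body system, relationship to study drug, severity of adverse event", among other factors. Subject incidence is divided by subjects exposed to drug, and episode incidence by doses.

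**Context.** Arm A receives rVWF plus TA and Arm B rVWF alone. The trial is open-label. Safety and tolerability of the combination against rVWF alone is a secondary objective. Section 4.6 does act on a single drug: after an allergic-type reaction during administration of either one, the subject "will immediately have that study drug stopped and appropriate medical care initiated".

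**The concern.** The pilot is meant to inform a larger trial on whether adding TA is safe and tolerated. A table of events by judged relationship is where a reader would look for events attributed to TA. With one joint rating, a related event in Arm A may have been blamed on TA, on the rVWF that both arms receive, or on either. In Arm B it can only mean rVWF, unless TA was given outside the randomised plan. The word therefore covers different exposures in the two arms. There is no TA-specific numerator, and no rVWF-specific numerator that pools cleanly across arms.

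Two further features make this worth settling before data collection. Staff who follow Section 4.6 must already decide which drug a reaction belongs to, but the written rating does not keep that decision. And two scales with different definitions are both said to apply to adverse events, so the table could change with the scale used to fill it.

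**Working it through.** The plan states no figure on this point, so there is none to reproduce. The check compares sections and does simple counting.

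**1. What a joint rating identifies.** The dosing schema in Section 3.2 gives 10 women per arm. Suppose k women in Arm A have at least one event rated related. The number with a TA-related event can be anything from 0 to k, so the TA-related proportion lies between 0/10 and k/10. For an assumed k of 3, that is 0% to 30%. The rating does nothing to narrow this.

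**2. Denominators.** Section 3.3 divides by women exposed and by doses. Under full dosing these differ by drug:

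| | Women | Doses |
|---|---|---|
| rVWF, Arm A | 10 | 10 × 3 = 30 |
| rVWF, Arm B | 10 | 10 × 3 = 30 |
| TA, Arm A | 10 | 10 × 1 = 10, up to 10 × 2 = 20 with the optional second dose |

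A joint numerator matches none of these rows in Arm A. Pooling the drugs gives 40 to 50 doses in Arm A against 30 in Arm B. Equal episode counts then give a per-dose rate in Arm A that is 1 − 30/40 = 25% to 1 − 30/50 = 40% lower.

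**3. The two scales side by side.**

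| | First scale | Second scale |
|---|---|---|
| *Possibly* | Reasonable timing; another cause may also explain the event | Reasonable timing or known pattern; no other cause reasonably explains it |
| *Related* | Improvement on stopping and return on re-exposure both needed | Return on re-exposure and/or improvement on stopping or dose reduction |
| Level without a counterpart | *Probably related* | *Unlikely* |

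Take an event with reasonable timing that the woman's clinical state is likely to have produced. On the first scale, timing rules out *not related*, and the event fits *possibly related*. On the second it fits *unlikely*. The *possibly* definition there joins its conditions with OR and then AND without brackets. If timing alone were read as enough, the same event would meet both *unlikely* and *possibly*. On either reading, related has no single definition.

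**4. Can the direction of a between-arm distortion be found?** As an illustration only, let r and t be the assumed chances that an event is attributed to rVWF and to TA, taken as independent, with identical events in both arms. The related share is 1 − (1 − r)(1 − t) in Arm A and r in Arm B. Assume one episode per woman and one TA dose, so 40 doses against 30.
- r = 0.10, t = 0.10: shares 0.19 and 0.10. Per dose, 1.9/40 = 0.048 against 1.0/30 = 0.033, higher in Arm A.
- r = 0.30, t = 0.10: shares 0.37 and 0.30. Per dose, 3.7/40 = 0.093 against 3.0/30 = 0.100, lower in Arm A.
- r = 0.30, t = 0: shares equal at 0.30. Per dose, 3.0/40 = 0.075 against 0.100, lower in Arm A.

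The sign changes with r, t and the denominator. The documents give neither r nor t.

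**The case against.** The best defence is that the comparison that matters does not need attribution. Section 5.0 has every adverse event recorded whatever its severity or relationship, the subject incidence in Section 3.3 is not filtered by causality, and TA is the only planned difference between arms. An all-cause comparison by arm therefore addresses the added effect of TA. This stands, and it limits the point to the relationship table. Section 3.3 does not, however, name the all-cause comparison as the main one.

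Three smaller defences also stand in part. Between-arm comparisons are descriptive only. The adverse event paragraph does not itself say that the relationship table is split by arm; that is inferred from the by-arm presentation planned earlier in Section 3.3. And the CRF is not in the documents, so it may hold a field per drug. If it does, Sections 3.3 and 5.0 still need to be aligned with it.

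A reader might go further and infer that the rating leans against TA, because Arm A has one more infusion soon after birth and timing decides the rating. The documents do not support this:
- They define no time window. Suppose an event counts if it starts within w hours of an infusion, with rVWF at hours 0, 24 and 48 and TA at the latest permitted +3 h. For w = 3, Arm A has 12 h against 9 h. With TA at +0.5 h the figures are 9.5/9 (+6%), 18.5/18 (+3%) and 36.5/36 (+1%) for w = 3, 6 and 12.
- On the per-dose rate, even the +3 h case shows no excess: 12/4 = 9/3 for w = 3. For w = 6 the Arm A windows total 9 + 6 + 6 = 21 h, and 21/4 = 5.25 is below 18/3 = 6.
- The upper levels of the first scale need more than timing. For *probably related*, the timing "is compelling, and the event cannot be explained by the subject's medical condition or other therapies".
- On the second scale as naturally read, an event that delivery itself explains is not *possibly* related in either arm.

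A reader might also infer that expedited reporting inherits the problem. The expedited test in the Data Safety Monitoring Plan asks about relation to study participation and does not cite this algorithm.

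**Conclusion.** The point holds for the table by relationship. Neither written scale asks for a rating per drug, so the table cannot isolate TA or give a drug-specific rate with a matching denominator. The TA-related proportion in Arm A is bounded only by 0 and the full related proportion. The two scales conflict on *possibly* and differ on *related*, so the table also lacks one definition.

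The size and direction of any distortion between arms cannot be determined from the documents. The comparison of all adverse events by arm is unaffected. The conclusion assumes 10 women per arm under full dosing, and that the CRF follows the written scales. It is a cheap improvement to a descriptive pilot and not a threat to its main safety comparison.

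**What to change.** 1. In Section 5.0, reconcile the two causality scales and keep one for all AEs and SAEs.
2. There and on the CRF, rate each event separately to rVWF and to TA, with the options *TA not given* and *cannot separate*. Base *TA not given* on what the woman actually received. Section 4.6 allows another hemostatic agent for a bleeding episode, so TA in Arm B is not ruled out by the text.
3. In Section 3.3, replace the single relationship table by two: rVWF-related events among women given rVWF, shown by arm, and TA-related events among women given TA. Give each its own subject and dose denominators, and report the *cannot separate* events alongside.
4. State in Section 3.3 that the safety comparison of Arm A with Arm B uses all adverse events regardless of judged relationship.

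The cost is one extra CRF item per event and some SAP wording. Some events will not be assignable to one drug, which the *cannot separate* option makes visible. The change is best made before the first event is rated, because attribution by drug is hard to recover reliably later.

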7.0 Data Sharing Plan

This study will be conducted in accordance with the following publication and data sharing policies and regulations per NIH Public Access Policy, which ensures that the public has access to the published results of NIH funded research. The final peer-reviewed journal manuscripts arising from this study will be submitted to the digital archive [PubMed Central](#) upon acceptance for publication. This study will also comply with the NIH Data Sharing Policy and Policy on the Dissemination of NIH-Funded Clinical Trial Information and the Clinical Trials Registration and Results Information Submission rule. As such, this trial will be registered at [ClinicalTrials.gov](#), and results information from this trial will be submitted to [ClinicalTrials.gov](#). In addition, every attempt will be made to publish results in peer-reviewed journals. Researchers will be able to locate and access data and/or other specimens from the VWD-WOMAN Trial by formal application to the VWD-WOMAN Trial Team.

8.0 Costs and Payments.

8.1 Research Study Costs. All costs associated with this study are experimental, as described below, including laboratory tests, out-patient hospitalization, study drugs, drug injections and infusions, blood sampling. The subject and insurer will not be billed for any research only services. The study will provide the study drug(s), rVWF (Vonvendi®) and TA (Cyclokapron®), drug administration, blood sampling, and coagulation testing at no cost. The subject and insurer will not be billed for any of these costs. The history and physical exam and monitoring will be provided at no cost by the investigators. Subjects or their third-party payer will be responsible for the costs associated with any routine medical care not part of this experimental study, should such costs arise. The subject will be responsible for any applicable copays, coinsurances and deductibles.

8.2 Research Study Payments. Subjects will receive remuneration for costs related to their participation

to help defray the cost of meals, travel, and time lost from work. There will be no additional costs to for participation in this study beyond the charges for routine medical care. The study will be funded by Takeda. Compensation is based on study visits completed. Subjects will receive \$50 for completing the initial screening visit (32-39 weeks' gestation); \$100 at admission for childbirth; and \$50 each at 1 day and 2 days postpartum; and \$150 on the Final Visit on Day 21, for a total of \$400.00. If a subject does not complete any part of the scheduled study visits, compensation for missed visits will not be made. Subjects will be paid upon completion of the study. If, for whatever reason a subject completes part, but not all of the study, the terms of payment will be determined by the visits completed.

9.0 Research Needs to be Provided by Investigator's Laboratory or Outside Laboratory: Von Willebrand factor assays (VWF:RCO, VWF:Ag, FVIII:C) and coagulation testing (fibrinogen, d-dimer) will be performed by the ITxM/ Vitalant Coagulation Laboratory under the direction of [name]; and blood counts (hemoglobin, hematocrit, platelets) and iron studies (Fe, TIBC, ferritin) will be performed by UPMC Clinical Laboratories.

10.0 Qualifications of Investigator.

[name] is a Clinical Instructor of Medicine in the Division of Hematology/Oncology , and is working with [name] and to conduct in the proposed trial. She has completed Research Fundamentals training.

[name] is an Assistant Professor of Medicine in the Division of Hematology/Oncology and engaged in research and patient care in VWD and other disorders of congenital hemostasis and thrombosis.

[name] is a Professor of Epidemiology and statistician at the Graduate School of Public Health Data Center where she has served as PI of Data Coordinating Centers (DCC) for NHLBI trials and has worked closely with [name] on several clinical trials in bleeding disorders.

APPENDIX

SCHEDULE OF EVENTS

Schedule of Events					
Study Week	-4	0	0	0	3
Study Visit	1	2	3	4	5
Event	32-39 Weeks'	Admission Childbirth	Day 1	Day 2	Day 21

	Gestation				
Screening, Consent	X				
Clinical Assessment					
Medical History	X		X	X	X
Vital Signs	X				
Mode of Delivery		X			
Randomization	X				
End of Study					X
Laboratory Assessment					
Blood Counts: Hemoglobin, Platelets	X	X	X	X	X
Iron Tests: Fe, TIBC, Ferritin	X				
VWF Assays: VWF:RCo, VWF:Ag, VIII:C	X	X	X	X	X
Coagulation Assays: Fibrinogen, D-dimer	X	X	X	X	X
Primary Endpoint Measure					
Quantitative Blood Loss at Delivery		X			
Secondary Endpoint Measures					
Lochial blood loss by PBAC			X	X	X
Diary: Blood products, transfusion, medications			X	X	X
Safety: Hysterectomy, thrombosis			X	X	X
Adverse Events					
Allergic reaction		X	X	X	X
Thrombosis		X	X	X	X
Bleeding (other)		X	X	X	X
